8.4.3 Exploratory Endpoints

1) Change in the biliary reflux symptoms from baseline at 3, 6, 9, and 12 months

For scores of questionnaire on bile reflux symptoms, the score of each typical symptom (upper abdominal pain, heartburn, nausea/sickness) and the total score of symptoms will be presented in three categories which are frequency, intensity, and the level of distress.

Protocol No.: DW_UDCA005 English Translation Version

The descriptive statistics (number of subjects, mean, standard deviation, median, minimum, and maximum values) of the baseline, at 3, 6, 9, and 12 months and variations from the baseline at 3, 6, 9, and 12 months for each treatment group are presented. The comparison between each treatment group of DWJ1319 versus the placebo is analyzed using the Analysis Of Covariance (ANCOVA) model, with the treatment groups (DWJ1319 600 mg/DWJ1319 300 mg vs Placebo) as the factor and the lymph node resection range (D1+, D2) and the type of gastrectomy (Total gastrectomy, partial gastrectomy) as the covariates. For the ANCOVA model results, present two-sided p-values for least-square mean (LSM), standard error (SE), and the corresponding 95% confidence interval of LSM difference of each treatment group (each treatment group of DWJ1319 - Placebo).

- 2) Percentage of subjects who experienced biliary reflux according to the upper gastrointestinal endoscopy at 3 and 12 months
- 3) Percentage of subjects who showed significantly abnormal AST and ALT values at 6 and 12 months

For the exploratory endpoints 2) and 3), the comparison between each treatment group of DWJ1319 versus the placebo is analyzed using the Logistic Regression Model, with the treatment groups (DWJ1319 600 mg/DWJ1319 300 mg vs Placebo) as the factor and the lymph node resection range (D1+, D2) and the type of gastrectomy (Total gastrectomy, partial gastrectomy) as the covariates. Logistic Regression Model results are presented as odds ratios, corresponding 95% confidence intervals and two-sided p-values.

A summary of the data is presented in the following tables.

- T. Change from Baseline in Biliary Reflux Symptom at 3, 6, 9, 12 month by Domain [Parameter: Symptom] (FAS)
- T. Change from Baseline in Biliary Reflux Symptom at 3, 6, 9, 12 month by Domain [Parameter: Symptom] (PPS)
- T. Change from Baseline in Biliary Reflux Symptom at 3, 6, 9, 12 month by Domain [Parameter: Domain] (FAS)
- T. Change from Baseline in Biliary Reflux *Symptom* at 3, 6, 9, 12 month *by Domain* [*Parameter: Domain*] (PPS)
- T. Change from Baseline in Biliary Reflux Symptom at 3, 6, 9, 12 month [Parameter: Total Score] (FAS)
- T. Change from Baseline in Biliary Reflux Symptom at 3, 6, 9, 12 month [Parameter: Total Score] (PPS)
- T. Percentage of Subjects with Biliary Reflux at 3, 12 month by Endoscopy (FAS)
- T. Percentage of Subjects with Biliary Reflux at 3, 12 month by Endoscopy (PPS)
- T. Percentage of Subjects with Clinically Significant result for AST at 6, 12 month (FAS)
- T. Percentage of Subjects with Clinically Significant result for AST at 6, 12 month (PPS)
- T. Percentage of Subjects with Clinically Significant result for ALT at 6, 12 month (FAS)
- T. Percentage of Subjects with Clinically Significant result for ALT at 6, 12 month (PPS)

Protocol No.: DW_UDCA005 English Translation Version

9. SAFETY EVALUATION

All safety assessment analysis is conducted on safety set.

9.1 Extent of Exposure

In terms of extent of exposure to the investigational product, for the Safety Set, the total dose (mg), exposure period (days) and average daily dose (mg/day) are presented with descriptive statistics (number of subjects, mean, standard deviation, median, minimum, and maximum values) for each treatment group.

A summary of the data is presented in the following tables.

- T. Extent to Exposure (Safety Set)

9.2 Adverse Events

Summary and analysis are performed for the Safety Set in cases where adverse events occurred after the administration of the investigational product or the severity of the preceding adverse events worsened (TEAEs: Treatment-Emergent Adverse Events) after the first dose of the investigational product.

All adverse events are standardized as "System Organ Class (SOC)" and "Preferred Term (PT)" using MedDRA version 20.0 or higher.

9.2.1 Overall Summary of Adverse Events

The number of subjects, expression rate (%) and the number occurrences of TEAEs and ADRs during the clinical study are presented as well as the 95% confidence intervals for the expression rate. However, a 95% accurate confidence interval for expression rate is presented when a cell with an expected frequency of less than 5 is equal to 20% or higher of all cells. The chi-square test or Fisher's exact test is used to determine whether there is a significant difference among the treatment groups, and the severity of the collected adverse events and their relevance to the investigational product are presented.

Also, serious adverse events, adverse events that resulted in permanent discontinuation of investigational product treatment, and adverse events that resulted in death are summarized.

A summary of the data is presented in the following tables.

- T. Overall Summary of TEAEs (Safety Set)
- T. Overall Summary of ADRs (Safety Set)

9.2.2 Display of Adverse Events

The number of subjects, expression rate (%) and the number of cases of all AEs and ADRs during the clinical study are presented according to SOC or PT. Also, the number of subjects, the expression rate (%) and the number of cases are presented for the severity (Mild/Moderate/Severe) according to SOC or PT.

If the same adverse events, based on "PT", occur multiple times in the same subject, treat it as one occurrence. If the severity and causal relationship are different, treat it with the maximum

Protocol No.: DW_UDCA005 English Translation Version

causal relationship and severity.

A summary of the data is presented in the following table and list.

- T. Incidence of Most Frequently Occurred(≥n%) TEAEs by SOC and PT (Safety Set)
- T. Incidence of Most Frequently Occurred(≥n%) ADRs by SOC and PT (Safety Set)
- T. Incidence of TEAEs by SOC and PT (Safety Set)
- T. Incidence of ADRs by SOC and PT (Safety Set)
- T. Incidence of TEAEs by Maximum Severity, SOC and PT: DWJ1319 600 mg (Safety Set)
- T. Incidence of TEAEs by Maximum Severity, SOC and PT: DWJ1319 300 mg (Safety Set)
- T. Incidence of TEAEs by Maximum Severity, SOC and PT: Placebo (Safety Set)
- T. Number of TEAEs by Severity, SOC and PT: DWJ1319 600 mg (Safety Set)
- T. Number of TEAEs by Severity, SOC and PT: DWJ1319 300 mg (Safety Set)
- T. Number of TEAEs by Severity, SOC and PT: Placebo (Safety Set)
- T. Incidence of ADRs by Maximum Severity, SOC and PT: DWJ1319 600 mg (Safety Set)
- T. Incidence of ADRs by Maximum Severity, SOC and PT: DWJ1319 300 mg (Safety Set)
- T. Incidence of ADRs by Maximum Severity, SOC and PT: Placebo (Safety Set)
- T. Number of ADRs by Severity, SOC and PT: DWJ1319 600 mg (Safety Set)
- T. Number of ADRs by Severity, SOC and PT: DWJ1319 300 mg (Safety Set)
- T. Number of ADRs by Severity, SOC and PT: Placebo (Safety Set)
- L. Subjects with TEAEs (Safety Set)
- L. Subjects with Pre-Treatment AEs (Safety Set)

9.2.3 Death and Serious Adverse Events and Other Significant Adverse Events

For the serious adverse events, adverse events that resulted in permanent discontinuation of investigational product administration, and adverse events that resulted in death, based on SOC or PT, the number of subjects, expression rate (%) and the number of cases are presented for each treatment group.

A summary of the data is presented in the following tables and lists.

- T. Incidence of Serious TEAEs by SOC and PT (Safety Set)
- T. Incidence of Serious ADRs by SOC and PT (Safety Set)
- T. Incidence of TEAEs Leading to IP Discontinuation by SOC and PT (Safety Set)
- T. Incidence of ADRs Leading to IP Discontinuation by SOC and PT (Safety Set)
- T. Incidence of TEAEs Leading to Death by SOC and PT (Safety Set)
- T. Incidence of ADRs Leading to Death by SOC and PT (Safety Set)
- L. Subjects with Serious TEAEs (Safety Set)

Protocol No.: DW_UDCA005 English Translation Version

- L. Subjects with TEAEs Leading To IP Discontinuation (Safety Set)
- L. Subjects with TEAEs Leading To Death (Safety Set)

9.2.4 Evaluation of Each Laboratory Parameter

For the continuous variables of the clinical laboratory test categories, descriptive statistics (number of subjects, mean, standard deviation, median, minimum, and maximum values) are presented for each treatment group with respect to the measured value and the change relative to the baseline at each visit. For intra-group changes relative to the baseline, paired t-test or Wilcoxon signed rank test is performed for comparison according to the result of the normality test. For the differences among the treatment groups, ANOVA or Kruskal-Wallis test is performed for comparison according to the result of the normality test.

A summary of the data is presented in the following tables.

- T. Summary of Hematology Data [Parameter] (Safety Set)
- T. Summary of Serum Chemistry Data [Parameter] (Safety Set)
- T. Summary of Urinalysis Data [Parameter] (Safety Set)

In order to confirm any changes in normality status after the administration of the investigational product compared to the baseline, data is divided into the normal, abnormal NCS and abnormal CS categories and summarized in shift table form by treatment group at each evaluation point. The McNemar's test is used for intra-group changes and the chi-square test or the Fisher's exact test is used to compare differences among the treatment groups. In addition, a list is presented of subjects who were normal or abnormal NCS at baseline but showed abnormal CS changes after administration of the investigational product.

A summary of the data is presented in the following table and list.

- T. Shift from Baseline at Post-Baseline on Hematology Data [Parameter] (Safety Set)
- T. Shift from Baseline at Post-Baseline on Serum Chemistry Data [Parameter] (Safety Set)
- T. Shift from Baseline at Post-Baseline on Urinalysis Data [Parameter] (Safety Set)
- L. Subjects Shifting from Normal or NCS at Baseline to CS at Post-Treatment on Laboratory (Safety Set)

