8.1. Inclusion Criteria

- 1) Patients who voluntarily agree to participate in the study and sign the informed consent form
- 2) Patients at least 19 years of age at the time of informed consent
- 3) Patients who were diagnosed with gastric cancer and underwent any one of the following gastrectomies
 - Total gastrectomy
 - Distal gastrectomy
 - Proximal gastrectomy
- 4) Patients who underwent D1+ or D2 lymph node dissection
- 5) Patients with ECOG performance status scale ≤ 1 point (Appendix 1)
- 6) Life expectancy of at least 3 months
- 7) Patients who can be enrolled in the study within 2 weeks from gastrectomy

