14.5. Safety Analysis

Safety analysis is performed for the safety analysis set. Safety endpoints are adverse events, laboratory tests, vital signs, and physical examinations. The baseline for each safety endpoint should use the results of the last assessment performed prior to the first dose of the investigational product.

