14.5.2. Laboratory Tests and Vital Signs

Descriptive statistics (mean, standard deviation, minimum, median, and maximum) will be presented by treatment group for the measurements at each time point and the change from baseline after the administration of the investigational product, and the frequency and proportion will be presented for categorical measurement results.

The treatment groups will be compared by ANOVA or a Kruskal–Wallis test for continuous data, and by the chi-square test or Fisher's exact test for categorical data.

For laboratory tests, classification should be made into a normal or not clinically significant abnormality and clinically significant abnormality. A shift table will be presented for changes in the post-administration compared to pre-administration of the investigational product. The chi-square test or the Fisher's exact test will be used to analyze the proportion of patients who have changed to clinically significant abnormalities post-dose at a not clinically significant abnormality.

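### SAP 9.2.4 and 9.3.1 add within-arm significance tests on laboratory values and vital signs against a baseline taken around gastrectomy; these p-values cannot address safety compared with placebo

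*Protocol*

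**What the plan says.** Protocol 14.5.2 plans descriptive statistics for values and changes from baseline, followed by comparisons between arms: "The treatment groups will be compared by ANOVA" or Kruskal-Wallis for continuous data, and chi-square or Fisher for categories. It plans no test within an arm.

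SAP 9.2.4 keeps the between-arm step: "For the differences among the treatment groups, ANOVA or Kruskal-Wallis test is performed for comparison according to the result of the normality test". Ahead of it, the SAP inserts a test inside each arm: "For intra-group changes relative to the baseline, paired t-test or Wilcoxon signed rank test is performed for comparison". SAP 9.3.1 says the same for vital signs. For the laboratory shift tables (normal, abnormal not clinically significant, abnormal clinically significant), SAP 9.2.4 adds McNemar's test within arms alongside chi-square or Fisher between arms.

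Protocol 14.5 sets the reference value: "The baseline for each safety endpoint should use the results of the last assessment performed prior to the first dose of the investigational product". Protocol 8.1 sets the timing: "Patients who can be enrolled in the study within 2 weeks from gastrectomy". Protocol 10.1 places randomisation itself within 2 weeks of surgery. SAP 11.1 (Significance Level) puts all tests at two-sided 0.05, and no adjustment is stated for the safety tests.

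**The concern.** The safety objective (protocol 5.1, SAP 3.2) is comparison with placebo. A paired test in one arm asks something else: whether that arm moved from its own baseline. Here the baseline is taken around major surgery, so arms can be expected to move whether or not the drug does anything.

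What is at stake is how the safety tables are read. Three columns of within-arm p-values invite the inference that a parameter changed on 600 mg but not on placebo. A significant result in one arm beside a non-significant one in another is not evidence of a difference between them.

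**Working it through.** **Sample sizes used.** The plan gives no figure for the safety tests, so I take its per-arm numbers. Its formula gives (1.96 + 0.842)² × (0.07 × 0.93 + 0.18 × 0.82) / 0.11² = 7.851 × 0.2127 / 0.0121 = 138.0, as stated. Dividing by 0.80 gives 172.5, rounded up to 173, as stated. The Safety Set is everyone dosed, so 173 is the upper figure per arm, and 138 allows for the planned 20% withdrawal.

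**Timing.** Routine laboratory baseline comes from Visit 1, at most 2 weeks before randomisation. Vital-sign baseline comes from Visit 2 (Day 1). Both lie close to gastrectomy, and follow-up runs from Month 3 to Month 12. Post-operative change is therefore part of the change from baseline in all three arms.

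**Number of tests.** SAP 6.5.6 lists 10 haematology items and 18 chemistry items that are measured repeatedly (HbA1c is taken once, at screening), so 28 analytes.

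- 28 analytes at Months 6 and 12: 28 × 2 = 56
- 5 liver tests at Months 3 and 9: 5 × 2 = 10
- 3 vital signs (systolic and diastolic pressure, pulse) at 4 visits: 3 × 4 = 12

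That makes 78 per arm and 78 × 3 = 234 in all. Urinalysis and McNemar tests are not counted. With no change anywhere, 234 × 0.05 ≈ 12 would be significant by chance.

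**Disagreement between arms when the drug does nothing.** Let d be the mean change divided by the SD of change, the same in every arm. The documents give no means or SDs, so d is assumed and shown over a range. The chance that one arm is significant is p = Φ(d√n − 1.96) + Φ(−d√n − 1.96). Arms contain different patients, so a given dose arm is significant and placebo is not with probability p(1 − p). Disagreement in either direction is 2p(1 − p).

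| d | n | p | dose significant, placebo not | either direction |
|---|---|---|---|---|
| 0.1 | 138 | 22% | 17% | 34% |
| 0.2 | 138 | 65% | 23% | 45% |
| 0.3 | 138 | 94% | 6% | 11% |
| 0.4 | 138 | >99% | <1% | <1% |
| 0.1 | 173 | 26% | 19% | 38% |
| 0.2 | 173 | 75% | 19% | 38% |
| 0.3 | 173 | 98% | 2% | 5% |
| 0.4 | 173 | >99% | <1% | <1% |

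**The retained between-arm test under the same conditions.** Simulated three-group ANOVA (4,000 runs per setting, d from 0.1 to 0.5, both sample sizes) flagged 4.3% to 5.0% of comparisons whatever the shared shift. It is not misled by post-operative change; the within-arm tests are.

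**The McNemar code.** SAP 15.2 cross-tabulates treatment by variable with the AGREE option. A within-arm shift test needs baseline category against post-baseline category. Elsewhere in SAP section 15, treatment denotes the arm, so the code as written does not perform the test described in 9.2.4. The shift table also has three categories, whereas McNemar's test is for two.

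**The case against.** The strongest reply is that nothing planned in the protocol has been lost. The sentence after the within-arm test keeps ANOVA or Kruskal-Wallis for the same parameters, and the shift tables keep chi-square or Fisher. The within-arm tests run in the placebo arm too, so recovery shows there as well, and the SAP nowhere says that a one-arm p-value will be taken as a drug effect. All of this stands. A reader might infer that the SAP has replaced or weakened the controlled comparison; it has not.

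Three other strong readings also go beyond the documents.

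- A reader might infer that every laboratory value gets a paired test. The test covers continuous variables only, and HbA1c has no follow-up value.
- A reader might expect arms to disagree often as a general matter. That holds only for small shared shifts, roughly 0.1 to 0.25 SD. A marked recovery would be significant in every arm, and the documents do not show how many parameters fall in each class.
- A reader might conclude that the addition is certainly undeclared. The visible part of the table in SAP section 14 lists only the gallstone-determination change, but the table is cut in the available text.

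It can also be said that labelling the p-values descriptive would be enough. That would limit misreading, but it would keep some 234 p-values that do not answer the stated objective.

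**Conclusion.** The point holds as a minor one. The SAP adds about 78 unadjusted within-arm tests per arm that the protocol does not plan and that cannot separate drug effect from post-operative change. With small shared shifts and no drug effect, a given dose arm looks changed while placebo does not in up to about a quarter of cases (23% at 0.2 SD with 138 per arm). With shifts of 0.4 SD or more nearly every arm is significant, which is equally uninformative. These percentages rest on an assumed common shift, the normal approximation and 138 to 173 patients per arm. The timing argument and the mismatch with the objective do not depend on them. The McNemar code is wrong for its stated purpose in any case. Only the reading of the laboratory and vital-sign tables is affected; the primary analysis is not.

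**What to change.** Delete the within-arm paired t, Wilcoxon and McNemar tests from SAP 9.2.4 and 9.3.1, and the matching code from 15.2. Keep descriptive change from baseline by arm, the shift tables and the between-arm tests. Add, for each continuous parameter and visit, the difference in change between each dose and placebo with a 95% confidence interval. This fits the safety objective more directly than a three-group ANOVA p-value.

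If the sponsor prefers to keep the within-arm tests, label them descriptive, list them in SAP section 14, and correct the McNemar code to compare baseline with post-baseline categories within each arm.

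The cost is SAP wording and table layout. No extra data or patients are needed.

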9.3 Other Safety Measures

9.3.1 Vital Signs

For the vital signs, descriptive statistics (number of subjects, mean, standard deviation, median, minimum, and maximum values) are presented for each treatment group with respect to the measured value and the change relative to the baseline at each visit. For intra-group changes relative to the baseline, paired t-test or Wilcoxon signed rank test is performed for comparison according to the result of the normality test. For the differences among the treatment groups, ANOVA or Kruskal-Wallis test is performed for comparison according to the result of the normality test.

A summary of the data is presented in the following table.

Protocol No.: DW_UDCA005 English Translation Version

- T. Summary of Vital Signs [Parameter] (Safety Set)

9.3.2 Physical Examination

For physical examination results at each visit, the number of subjects and percentage (%) are presented for normal, abnormal NCS, and abnormal CS categories, and a list is presented for subjects who were indicated as abnormal CS. If the same adverse events, based on "PT", occur multiple times in the same subject, treat it as one occurrence. If the severity and causal relationship are different, treat it with the maximum causal relationship and severity.

A summary of the data is presented in the following table and list.

- T. Physical Examination (Safety Set)
- L. Subjects with Abnormal CS on Physical Examination (Safety Set)

Protocol No.: DW_UDCA005 English Translation Version

10. ADDITIONAL EVALUATION

NA

11. GENERAL PRESENTATION OF SUMMARIES AND ANALYSES

11.1 Significance Level

Unless otherwise specified, all tests are set at a significance level of 0.05 and are subject to testing on two-sided tests in principle.

11.2 Summary Statistics

Unless otherwise specified, the number of subjects, mean, standard deviation, median, minimum, and maximum values are presented for continuous variables, and frequency and percentage (%) are presented for categorical data.

11.3 Decimals

When descriptive statistics such as number of subjects, mean, standard deviation, median, minimum, and maximum values are presented in percentage (%) for the continuous variables, it is presented up to two decimal places. For p-value, it is displayed up to four decimal places. If the calculated p-value is less than 0.0001, it is presented as '<0.0001'.

Summaries of vital signs and clinical laboratory tests are rounded to the number of significant digits, that is, the maximum number of digits below the decimal point for each item.

11.1 Statistical Analysis Methods

When a confidence interval for a ratio is presented, an accurate confidence interval is presented when a cell with an expected frequency of less than 5 is equal to 20% or higher of all cells. In addition, if the odds ratio is estimated to be infinite including the cell with a frequency of 0 when presenting the odds ratio, the odds ratio is estimated using Firth's Penalized Maximum Likelihood and a profile-likelihood confidence interval is presented.

